6.2 Definition and Assessment of (Serious) Adverse Events and Other Safety Related Events

An AE is any untoward medical occurrence in a subject or a clinical investigation subject administered a pharmaceutical product, and which does not necessarily have a causal relationship with the trial procedure. An AE can therefore be any unfavorable and unintended sign (including an abnormal laboratory finding), symptom, or disease temporally associated with the use of a medicinal (investigational) product, whether or not related to the medicinal (investigational) product. [\[ICH E6\(R2\), 2016\]](#)

The sources of AEs include:

- The subject's response to questions about his/her health (a standard non-leading question such as "How have you been feeling since your last visit?" is asked at each visit)
- Symptoms spontaneously reported by the subject
- Investigations and examinations with findings that are assessed by the Investigator to be clinically significant
- Other information relating to the subject's health becoming known to the Investigator

For surgical or diagnostic procedures, the condition/illness leading to such a procedure is considered as the AE rather than the procedure itself.

An SAE is classified as any untoward medical occurrence that:

- Results in death
- Is life-threatening
- Requires in-patient hospitalization or prolongation of existing hospitalization
- Results in persistent or significant disability/incapacity

- Is a congenital anomaly/birth defect in a neonate/infant born to a mother exposed to IMP (also applies if father was exposed to IMP)
- Is a medically significant event in the Investigator's judgment (e.g., may jeopardize the subject or may require medical/surgical intervention to prevent one of the outcomes listed above) [ICH E2A, 1995]

Medical conditions present at the initial trial visit that do not worsen in severity or frequency during the trial are defined as baseline medical conditions (medical history) and are not to be considered AEs.

6.2.1 Events that Do Not Meet the Definition of an SAE

Elective hospitalizations to administer, or to simplify trial treatment or trial procedures are not considered SAEs. However, all events leading to unplanned hospitalizations or unplanned prolongation of an elective hospitalization (e.g., undesirable effects of any administered treatment) must be documented and reported as SAEs.

Events that do not meet the definition of an SAE:

1. Hospitalization or prolongation of hospitalization as part of a routine procedure
2. Hospitalization for a survey visit, annual physicals or social reasons
3. Hospitalization that does not include an overnight stay
4. Elective hospitalizations for pre-existing conditions documented in the medical history that have not worsened

In case of doubt, an event should be reported within timelines.

6.2.2 Adverse Events of Special Interest

An AESI, serious or non-serious, is an AE of scientific and medical concern specific to the Sponsor's product or program, for which ongoing monitoring, additional information, and rapid communication by the Investigator to the Sponsor can be appropriate. Depending on the nature of the event, rapid communication by the trial Sponsor to other parties (e.g., regulators) might also be warranted in line with Council for International Organizations of Medical Sciences standards and local regulations.

The following are considered AESIs for this trial and should be communicated by the Investigator to the Sponsor within 2 weeks following the event:

Injection site reactions

Subjects will be monitored for injection site reactions (ISR) for at least 1 hour after each IMP administration given at site, during a trial visit at the site, or longer (i.e., until the reaction stops or the subject leaves the site), as necessary. Where IMP administration is administered by the subject, or by a family member/caregiver, the subject will be instructed to monitor and report ISRs according to instructions in the Trial Medication Manual for Subjects. Injection site reactions will be reported as AEs. The individual symptoms of the ISR (e.g., injection site pain, injection site pruritus [itching], injection site erythema [redness], injection site edema [swelling], and injection site bruising) should be reported as AEs. For administrations at the subject's home, the subject will be trained when to contact the Investigator (or a physician) immediately, depending on reaction severity.

Data on local tolerability will be collected as an AESI. The following characteristics of ISRs will be documented:

- Pain
- Erythema
- Induration
- Pruritus
- Bruising

Severity and duration of these features of the ISR will be collected by the site by direct observation when IMP is administered on site. When IMP is administered at home, ISRs should be reported to the site for documentation in the subject's source documents and entry into the eCRF.

Table 5: Grading of Severity is based on NCI-CTCAE version 5.0 in line with other AEs in this trial

Pain	
Grade 1	Mild pain
Grade 2	Moderate pain; limiting instrumental activities of daily living
Grade 3	Severe pain; limiting self-care activities of daily living
Pruritus	
Grade 1	Mild, localized reaction with only topical intervention
Grade 2	Moderate with noticeable skin change from scratching (e.g., excoriation). Oral therapy indicated
Grade 3	Widespread and resulting in treatment interruption
Induration	
Grade 1	Mild induration with skin able to slide and pinch up
Grade 2	Unable to pinch up skin but still slides
Grade 3	Severe, unable to slide or pinch, potentially limiting activity of daily living and consideration of treatment interruption
Erythema	
Grade 1	Mild, <2.5 cm
Grade 2	Moderate, 2.5–5 cm
Grade 3	Severe, >5 cm
Bruising	
Grade 1	Mild, <2.5 cm
Grade 2	Moderate, 2.5–5 cm
Grade 3	Severe, >5 cm

NCI-CTCAE, National Cancer Institute – Common Terminology Criteria for Adverse Events

Gastrointestinal Obstruction

Any GI obstructions will be treated by the Investigator according to the Investigator's judgment and carefully followed up.

Gallbladder, Biliary and Pancreatic Disease

These should be monitored by symptoms, liver enzymes (ALT, AST, GGT, alkaline phosphatase), bilirubin, lipase and amylase and subjects should be treated according to the Investigator's judgment.

Fluid Overload

Subjects will be monitored closely for signs and symptoms related to fluid overload, e.g., edema, due to increased absorption. The Investigator will document cases of substantial fluid overload and manage as per clinical practice for the subject accordingly.

Colorectal Polyps

Where deemed anatomically feasible by the Investigator, two gastroduodenoscopies and colonoscopies or colonographies will be done during the course of the trial, one before enrolment and one at the end of the trial. Any polyps found during colonoscopies must be removed, and the histology documented in the source documents and eCRF.

Malignancies

For any subject with a malignancy identified during the course of the trial, a thorough medical history will be taken and documented (e.g., smoking history for lung cancer). Information on type of malignancy, histological type and grading will be collected. The IMP treatment will be discontinued, and the subject will be closely followed up by the Investigator.

Once the clinical database containing all AEs is available, potential AESIs will be identified using the following algorithmic standardized Medical Dictionary for Regulatory Activities (MedDRA) queries (including Standardized MedDRA Queries (SMQs)):

- Standardized MedDRA Queries Functional, inflammatory and gallstone related biliary disorders
- Standardized MedDRA Queries GI perforation, ulceration, hemorrhage or obstruction
- Standardized MedDRA Queries Malignancies

In the absence of related SMQs, customer queries (CQs) will be set up from the Sponsor-defined list of preferred terms (PTs) as listed in the Statistical Analysis Plan (SAP).

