- If at any visit the subject shows signs of significant fluid overload, leading to clinical decompensation, the Investigator should consider PS reduction. An AESI of fluid overload must be reported. In all cases this reduction must be discussed with the medical monitor either before or after reduction
- Patient reported outcomes collected as follows (with the following preferred order):
 - At Baseline: SBS-IF-CIC-QOL, PGI-S, PGI-PSI, PGI-SPS, PGIC (1.0), PGIC (2.0)
 - At Weeks 4, 12, and 36: SBS-IF-CIC-QOL, SBS-IF-T1-QOL, PGI-S, PGI-PSI, PGI-SPS, PGIC (1.0), PGIC (2.0)
 - At Weeks 24, 52, and EOT visit: SBS-IF-CIC-QOL, SBS-IF-T1-QOL, PGI-S, PGI-PSI, PGI-TS, PGI-SPS, PGIC (1.0), PGIC (2.0)
 Only subjects that completed version 1.0 of the PGIC and PGI-S at baseline continue to complete these during the trial
- See [Table 2](#) Schedule of Assessments for metabolic balance periods
- The visit window of ± 1 week or ± 2 weeks allows a shift in the visit 7 or 14 days (± 1 day) from Baseline calculated visits. Visits should be done at the same day of the week with a window of ± 1 day. Investigational medicinal product administrations during a week with a site visit must be done at the site
- If biopsies are required a colonoscopy will NOT be performed unless a full view of the colon to check for polyps was not possible during the colonoscopy
- Optional assessments
- When deemed anatomically feasible by the Investigator, colonoscopy or colonography should be performed within ± 3 weeks of end of treatment
- ECG, physical exam and vital signs should be recorded prior to blood sampling and prior to IMP administration
- Subjects to be asked to measure their body weight weekly and record results in the e-diary. Body height will be measured once at screening only
- Adverse events and AESIs should be recorded starting after obtaining informed consent (see [Section 6.1](#))
- Telephone contact will be made every 7 days (± 1 day) during screening. During each contact, AEs will be collected and changes in concomitant medications recorded
- At all contacts the subject will be asked to recollect the frequency and severity of nausea, vomiting, and abdominal pain in the preceding 7 days. This information will also be collected at Visit 3, pre-dose. At Week 0, Day 1 (± 1 day), the subject will be contacted to assess for fluid overload and frequency of stools

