5.2.8 Visit 18 (End-of-Trial Visit)

This visit is scheduled at 4 weeks after last dose of IMP for all subjects who opt not to participate in the LTE. In case a subject terminates the trial prematurely for whatever reason, this visit will be scheduled as an EOT visit at 4 weeks after the final IMP dose.

- Data will be recorded for:
 - Changes in concomitant medications
 - Prescribed PS volume and composition
 - Change in eating/appetite
 - Patient reported outcomes
 - Investigator narrative
- A colonoscopy including removal of any polyps or colonography will be done within ± 3 weeks of the EOT visit, only for subjects that terminate early. The assessment will be done only if they have received at least 8 weeks of treatment (i.e., eight doses).
- Full physical examination
- Twelve-lead ECG
- Vital signs (systolic and diastolic blood pressure, heart rate, and axillary temperature)
- Body weight
- Blood samples will be collected for:
 - Clinical chemistry including liver enzymes
 - Hematology
 - Hemostasis
 - Pharmacokinetics
 - Citrulline
 - Anti-drug antibodies
 - Serum pregnancy test for premenopausal women
- Urine sampling for urinalysis
- Any new AEs will be recorded and assessed, and existing AEs will be followed up (see Section 6)

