8. ANALYSIS POPULATIONS

Analyses of efficacy and PRO will be based on the Full Analysis Set (FAS; See definition below), whereas all the rest of analyses will be based on the Safety Analysis Set (SAS; See the definition below), except for the summary table for all screened subjects and for the disposition table, which will be based on SAS as well as FAS.

To help characterize the FAS, tables for demographics & other baseline characteristics, concomitant diseases and medications, and treatment exposure & compliance will be repeated by FAS. The additional changes to this plan can be found in [Appendix 4: Addendum to Statistical Analysis Plan](#).

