9.8.4 VITAL SIGNS AND OTHER SAFETY PARAMETERS

For vital signs (systolic and diastolic blood pressure, heart rate, and temperature) and weight, summary statistics of observed and changes from baseline values will be presented by analysis visit up to Week 52.

All height, weight, and vital signs data will be listed.

Similarly, for each electrocardiogram (ECG) parameter (RR interval, PR interval, QRS interval, QT interval, QTcF interval), summary statistics of observed and changes from baseline values will be presented by analysis visit. In addition, ECG interpretation results will be summarized by frequency (%) for each analysis visit up to Week 52.

All ECG data will be listed.

All physical examination data will be listed.

The relative change from baseline in urine volume (%) will be summarized by analysis visit up to Week 52. The change from baseline and percent change from baseline will be calculated using the average daily urine volume data as per the Balance Period Calculations eCRF.

Subject data listings will be prepared to document data from the 48-hour urine collection diary, 24-hour urine collection diary, balance period calculations, post-PS volume reduction safety evaluation, and PS adjudication.

There will be a separate listing to document PS volume details upon withdraw from trial visits for subjects who have permanently discontinued from trial treatment.

The investigator narratives data will be listed.

Colonoscopy/colonography data will be listed.

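### The colorectal-polyp AESI rate has no examined-subject denominator, although post-baseline colon examination is conditional, so as visible the SAP would most likely count unexamined subjects as polyp-free

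*Protocol*

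**What the plan says.** Protocol 1.5.2.1 and 7.1.1 and SAP 7.1 list colorectal polyps among the AESIs that form part of the primary endpoint. The SAP introduction states that all subjects are analysed under protocol version 4, where safety is the primary objective.

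**Who is examined.**
- Protocol 6.2.2 plans one examination before enrolment and one at the end of the trial, subject to feasibility: "Where deemed anatomically feasible by the Investigator, two gastroduodenoscopies and colonoscopies or colonographies will be done during the course of the trial".
- A footnote to Table 1 of the protocol repeats the condition for the later examination: "When deemed anatomically feasible by the Investigator, colonoscopy or colonography should be performed within ± 3 weeks of end of treatment". Protocol 5.1.10.1 has the same condition.
- The Week 24 examination carries the footnote "Optional assessments".
- For subjects who stop early, Protocol 5.2.8 adds: "The assessment will be done only if they have received at least 8 weeks of treatment", which it equates with eight doses.

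**Who is in the denominator.**
- SAP 8 bases efficacy and PRO analyses on the Full Analysis Set, "whereas all the rest of analyses will be based on the Safety Analysis Set". SAP 8.2 defines that set by exposure alone.
- SAP 9.8.2 asks for the incidence (%) of subjects with treatment-emergent AESIs and names neither a denominator nor an examined subset.
- SAP 9.1 has a general rule that, unless otherwise specified, post-baseline percentages use subjects with non-missing values in the relevant analysis set.
- SAP 9.8.4 says of the examinations themselves only: "Colonoscopy/colonography data will be listed".

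**What cannot be seen.** The SAP introduction says that a Note to File of 6 December 2022 supersedes other sections of the SAP and the table shells. SAP 6, 8 and 9.8.2 point to it, but Appendix 4 gives only a reference. The table shells are in a separate document.

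**The concern.** Most AESIs in this trial come to light through symptoms, signs or laboratory values. For polyps, Protocol 6.2.2 describes only endoscopy or colonography. A dosed subject with no colon examination after baseline has unknown polyp status, not negative status. If that subject stays in the denominator, the reported percentage falls below the rate among subjects whose colon was inspected, and a count of zero looks more reassuring than the data allow.

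The point has some weight here because Protocol 1.7.1 names enhanced colon polyp growth as a treatment-related risk of the marketed drug in this class, linked to its mode of action. Protocol 2.1 says the completed apraglutide trials enrolled subjects with stoma and that this trial should help show whether the safety profile differs when the colon is in continuity. Every subject here retains colon, so this is an AESI on which the trial can add information.

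**Working it through.** The documents state no polyp rate and no expected number examined, so there is no figure of the plan's own to reproduce.

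**Inputs**
- Enrolled: 2 + 7 = 9 (SAP introduction). I assume all nine were dosed, so the Safety Analysis Set is 9.
- Examined at least once after baseline, *m*: not in the documents. I take *m* from 9 down to 5.
- Only planning figure: 10 enrolled, eight expected to complete (Protocol 7.2).

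**Step 1: does the SAP 9.1 rule already give an examined-subject denominator?** The rule needs a non-missing value per subject. Adverse events are stored as records of events. A subject without a polyp record looks the same whether the colon was clear or never inspected, so there is no missing value to trigger the rule. Where the SAP wants an assessed-subject denominator for a safety table it writes one out: SAP 9.8.3 for laboratory shift tables and SAP 9.8.5 for antibody results. SAP 9.8.2 has no such sentence. The likely reading is the full Safety Analysis Set, but the text does not say so outright.

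**Step 2: direction and size.** If *m* of 9 are examined and *x* have a polyp, the rate over all exposed is *x*/9 and the rate over examined subjects is *x*/*m*. Their ratio is *m*/9, which cannot exceed 1, so any error is an understatement. For *m* = 8, 7, 6 and 5 the ratio is 0.89, 0.78, 0.67 and 0.56.

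**Step 3: one event and no event.** Intervals are two-sided exact 95% (Clopper-Pearson). With no event the upper limit is 1 − 0.025^(1/*m*); for *m* = 9 this is 1 − 0.025^(1/9) = 0.336.

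| Examined *m* | One event, 1/*m* (95% CI) | No event, 95% upper limit |
|---|---|---|
| 9 (same as all exposed) | 11.1% (0.3–48.2) | 33.6% |
| 8 | 12.5% (0.3–52.7) | 36.9% |
| 7 | 14.3% (0.4–57.9) | 41.0% |
| 6 | 16.7% (0.4–64.1) | 45.9% |
| 5 | 20.0% (0.5–71.6) | 52.2% |

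**Step 4: the planning figures.** If only the eight expected completers of 10 were examined, one event would be 1/10 = 10.0% against 1/8 = 12.5%. With no event the upper limit would be 30.8% against 36.9%. Completers are only a rough stand-in for examined subjects: a completer may be unexaminable, and a non-completer with eight or more doses may be examined.

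**The case against.** The strongest reply is that the denominator is not visible enough to criticise. The Note to File overrides the SAP, and the SAP refers to it on populations and on AESIs. SAP 10 describes one AESI change in it, identification by the investigator's assessment in the eCRF, which does not settle who was examined; the rest is unknown. The end-of-treatment examination in Table 1 also carries a footnote whose text is blacked out. This stands as a limit on certainty. A reader might infer that the plan expressly prescribes an all-exposed denominator for polyps. It does not: that follows from SAP 8 together with the silence of SAP 9.8.2, and SAP 9.1 leaves some ambiguity.

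A second reply is that few subjects may go unexamined. Willingness to undergo colonoscopy or colonography is an inclusion criterion, there are two alternative methods, Week 24 offers a further optional examination, and early terminators with at least eight doses are still covered. This also stands. A reader might take the lower rows of the table as expected values, but nothing in the documents supports five, six or seven examined rather than eight or nine.

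Third, a reader might infer that a colon examination is the only way to produce an event in this category. SAP Appendix 3 does not support that: its colorectal-polyp list includes gastric, duodenal and oesophageal terms, and gastroduodenoscopy is also scheduled. Any rate over colon-examined subjects must therefore count colorectal events only.

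Last, the trial is descriptive, no test or decision rule uses this rate, all-exposed denominators are usual for adverse events, and with nine subjects the listings allow the count to be rebuilt by hand. That is why this is an improvement to the tables and not a defect that threatens the trial. It does not help someone who reads only the summary table.

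**Conclusion.** The point holds in a limited form. Post-baseline colon examination is conditional, the visible SAP defines no examined-subject denominator for colorectal polyps, and no planned table shows how many subjects were examined. The plan as visible would most likely count unexamined subjects as polyp-free, and any resulting error can only understate the rate.

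The size depends on a number the documents do not give. With eight of nine examined the change is small: 11.1% to 12.5% for one event, and 33.6% to 36.9% for the upper limit with none. With five of nine it is 11.1% to 20.0% and 33.6% to 52.2%. If all nine are examined there is no difference, and the added row simply documents complete ascertainment. These figures assume that all nine enrolled subjects were dosed and that the Note to File does not already set a different denominator.

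**What to change.** Keep the AESI row based on the Safety Analysis Set and add one row for colorectal polyps:
- Numerator: subjects with a colorectal event, leaving out the upper-gastrointestinal terms in SAP Appendix 3.
- Denominator: subjects with at least one evaluable post-baseline colonoscopy or colonography, counting the optional Week 24 examination.
- Also show the number examined by method, the number not examined, and an exact 95% CI for the rate.

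State in SAP 9.8.2 which denominator each row uses, and confirm that this agrees with the Note to File and the table shells. The examination schedule does not change. The data are already collected, so the cost is one more table row. The downside for the sponsor is a figure that may look slightly less favourable.

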6.2.3 Assessment of Causality

Both Investigator and Sponsor will assess the causality of the event in relation to the IMP, based on the criteria listed in the [ICH E2A](#) guidelines:

Investigators must also systematically assess the causal relationship of AEs to IMP(s)/trial treatment (any other non-IMPs, radiation therapy, etc.) using the following definitions. Decisive factors for the assessment of causal relationship of an AE to the IMP include, but may not be limited to, temporal relationship between the AE and the IMP, known side effects of IMP, medical history, concomitant medication, course of the underlying disease, trial procedures.

Table 6: Assessment of Causality of Adverse Events

	Assessment of Causality				
	Definitely	Probably	Possibly	Unlikely	Unrelated
Clearly due to extraneous causes	N	N	N	N	Y
Reasonable temporal association with drug administration	Y	Y	Y/N	N	N
May be produced by subject clinical state, etc.	N	N	Y	Y	Y
Known response pattern to IMP	Y/N	Y/N	N	N	N
Disappears or decreases on cessation or reduction in dose	Y	Y/N	N	N	N
Reappears on re-challenge (if possible)	Y	N	N	N	N

IMP, investigational medicinal product; Y, yes; N, no

Not related: Not reasonably related to the IMP. Adverse event could not medically (pharmacologically/clinically) be attributed to the IMP under trial in this clinical trial protocol. A reasonable alternative explanation must be available. Adverse events reported as “unlikely” related and “unrelated” will be considered unrelated for reporting purposes.

Related: Reasonably related to the IMP. An adverse event could medically (pharmacologically/clinically) be attributed to the IMP under trial in this clinical trial protocol. [Table 6](#) can be used to differentiate between the AEs related to the IMP. Adverse events reported as definitely, probably and possibly related will be considered as “related” for reporting purposes.

